9.3 Analyses Sets

The analysis sets are specified below. The final decision to exclude participants from any analysis sets will be made during a data review meeting prior to database lock.

Analysis Set	Description
Screening (SCR)	All participants, who provided informed consent, regardless of the participant's enrollment and study intervention status in the study.
Safety (SAF)	All participants, who were administered any dose of any study intervention. Analyses will consider participants as treated.
Pharmacokinetic (PK)	The PK Analysis Set is a subset of the SAF, and the PK population will include all participants: Who have completed the study without any relevant protocol deviations and factors likely to affect the comparability of PK results. With adequate study intervention compliance. With evaluable PK data, i.e., nonmissing values for primary endpoints. If participants received prohibited concomitant therapy or medicines, as specified in Section 6.8.3, they will be excluded from the PK population. All PK analyses will be based on this analysis set.

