1.2 Schema

1.3 Schedule of Activities

Assessments & Procedures	Screening	Intervention Period (Days)																			Safety Follow Up	Notes	
		-1	1	2	3	4	5	6	7	8	9	10	11	12	13	14	15	16	17	18	19		
Study Day	-28 to -2																						
Informed consent	X																						Prior to any Screening activity.
Participants resident at CRU		X	X	X	X	X							X	X	X	X	X						
Ambulatory visits at CRU							X	X	X	X	X							X	X	X	X	X	
Eligibility criteria	X	X																					Recheck of eligibility criteria on Day -1, (Sections 5.1 and 5.2).
Demography, height & weight	X																						Demography to include, at minimum, age (year of birth), sex, race, and ethnicity.
Medical history	X																						
Physical examination	X	X										X								X			Brief examination on Day -1 to check eligibility. Section 8.2.1.
Serum pregnancy test	X	X																			X		Section 8.3.4 and Appendix 5.
FSH	X																						In postmenopausal women, only (Appendix 5).
Viral serology, TSH	X																						Appendix 5.
Clinical laboratory tests (blood and urine)	X	X										X		X	X	X	X				X		Details in Appendix 5.
Cotinine, drug screen, alcohol breath test, SARS-CoV-2	X	X											X										Details in Appendix 5.
Vital signs & safety ECG	X	X	X	X									X	X	X	X	X				X		Predose on dosing days. Sections 8.2.2 and 8.2.3.

Assessments & Procedures	Screening	Intervention Period (Days)																				Safety Follow Up	Notes
		-28 to -2	-1	1	2	3	4	5	6	7	8	9	10	11	12	13	14	15	16	17	18	19	
Study Day	-28 to -2																						
AE/concomitant medication review	X	X	X	X	X	X	X	X	X	X	X	X	X	X	X	X	X	X	X	X	X	X	Section 6.8. Section 8.3.
CCI [REDACTED]			C																				CCI [REDACTED]
Itraconazole administration												X	X	X	X	X	X	X	X	X	X	X	Once daily with food (Section 5.3.1 and Section 6.1).
Tepotinib administration				X											X								Section 5.3.1. Section 6.1.
CCI [REDACTED]				X	X	X	X	X	X	X	X				X	X	X	X	X	X	X	Detailed PK sampling scheme in Table 1.	
Fecal sampling			X	X	X	X									X	X	X	X					All stools during the stay at CRU to be collected (Section 8.4).
Mild laxative					X											X							To be administered in the evenings (Section 8.4).

AE=adverse events, CRU=clinical research unit, ECG=electrocardiogram, FSH=follicle stimulating hormone, PK=pharmacokinetics, SARS-CoV-2=severe acute respiratory syndrome coronavirus type 2, TSH=thyroid stimulating hormone.

Table 1 **Tepotinib and Metabolite PK Sampling Schema**

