6.8.2 Permitted Medicines

The only permitted medications are the following:

- Paracetamol/acetaminophen up to 2 g per day, at the discretion of the Investigator.

Any medicines that are considered necessary to protect the participant's welfare in emergencies may be given at the Investigator's discretion, regardless if it results in a protocol deviation.

Medications may be given at the Investigator's discretion if deemed necessary for the participant's immediate wellbeing. Medications may be administered to address adverse reactions or anticipated emergency situations.

The Investigator will record all concomitant medications taken by the participants during the study, from the date of signature of informed consent, in the participant source data and in the appropriate section of the eCRF.

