6.8.3 Prohibited Medicines

Prohibited medicines at study entry are indicated in the exclusion criteria (Section [5.2](#)).

The participants are prohibited from using prescription or over-the-counter medications (apart from those described above) within 2 weeks or 5 terminal half-lives, whichever is longer, prior to the first administration of study intervention, during the study, and until the Safety Follow Up Assessment (this includes herbal remedies, vitamins, minerals, antacids and dietary supplements such as fish oils).

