AUC _{extra%}	The AUC from time t_{last} extrapolated to infinity given as percentage of $AUC_{0-∞}$. $AUC_{extra\%} = (\text{extrapolated area}/AUC_{0-∞}) \times 100$.
	CCI [REDACTED] [REDACTED] [REDACTED]
	[REDACTED] [REDACTED] [REDACTED]

- Whole blood samples of approximately 2 mL per collection for measurement of plasma concentrations of tepotinib and its CCI CCI will be collected. Collection times are specified in the Schedule of Assessments (Section 1.3) and Table 1. The actual date and time (24-hour clock time) of each sample will be recorded to calculate actual time elapsed since the prior dose administration.
- The quantification of tepotinib and its CCI CCI in plasma will be performed using a validated assay method. Concentrations will be used to evaluate the PK of tepotinib and its metabolites.
- Remaining samples collected for analyses of tepotinib concentration may also be used to evaluate safety or efficacy aspects related to concerns arising during or after the study.
- Details on processes for collection and handling of these samples are in the Laboratory Manual. Retention time and possible analyses of samples after the end of study are specified in the respective ICF.
- PK parameters will be derived using noncompartmental methods with the validated computer program.

The exact date and time of sample collection and study intervention (24-hour clock time) must be recorded in the eCRF and will be used in the calculation of PK parameters. The accepted time deviations from planned tepotinib PK times that will not be considered a protocol violation are listed below (Table 2).

Table 2 PK Sampling Time Windows

Procedure	Time Point (Relative Time)	Window Allowance
Pharmacokinetics	Predose	- 60 min
	1 to 12 hours postdose	- 5 / + 5 min
	> 12 to 24 hours postdose	- 30 / + 30 min
	> 24 to 72 hours postdose	- 60 / + 60 min
	> 72 to 168 hours postdose	- 180 / + 180 min

Any deviation from the above-mentioned time windows requires a comment in the eCRF and may be discussed in the data review meeting.

Collection of Feces for Pharmacokinetic Analysis

In both in-house periods of the study, all feces after administration of tepotinib until discharge from the CRU (i.e., from Day 1 to Day 4, and from Day 12 to Day 15) will be collected for exploratory tepotinib pharmacokinetic analysis.

- To ensure defecation, participants will receive a mild laxative on the evenings of Day 3 and Day 14.

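### Does the rule on prohibited medicines put the primary PK analysis set at risk, given the scheduled laxative, the Day 20 window and the unstated order of exclusions?

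*Protocol*

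**What the plan says.** **Set definition.** Protocol 9.3 and SAP 8.1 define the PK set in the same terms. One criterion is conditional on relevance: "Who have completed the study without any relevant protocol deviations and factors likely to affect the comparability of PK results". The sentence on medicines is not: "If participants received prohibited concomitant therapy or medicines, as specified in Section 6.8.3, they will be excluded from the PK population". All PK analyses, including the primary one, use this set. Protocol 9.3 adds: "The final decision to exclude participants from any analysis sets will be made during a data review meeting prior to database lock".

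**What is prohibited.** Protocol 6.8.3 bars prescription and over-the-counter products other than those in the preceding section, with vitamins and supplements included in the ban. It applies before first dosing, "during the study, and until the Safety Follow Up Assessment". Section 6.8.2 opens with "The only permitted medications are the following" and lists paracetamol alone. It then allows discretionary medicines for emergencies and immediate wellbeing, and also: "Medications may be administered to address adverse reactions or anticipated emergency situations".

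**What is scheduled.** Protocol 8.4: "To ensure defecation, participants will receive a mild laxative on the evenings of Day 3 and Day 14". The Schedule of Activities carries the same item.

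**Value-level exclusions.** SAP 10.2.1 names concomitant medication and supplements among events whose effect on PK is discussed at the data review meeting; flagging individual values is given as an example of the action. SAP 16.1.4 removes affected concentrations and parameters from summaries and further analysis.

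**The concern.** The rule decides who enters the only set used for the primary endpoints, and three features of it look unsafe.

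1. **Laxative.** A routine dose given to everyone is not on the permitted list, and it is not an emergency, a wellbeing measure or treatment of a reaction. On a literal reading each participant has received a non-permitted medicine, and the PK set is empty.
2. **Window.** The ban ends at Safety Follow Up on Day 20, while the last PK sample is on Day 19. A vitamin first taken after that sample cannot alter either profile, yet it would cost a complete pair of profiles.
3. **Order.** The same vitamin could lead to removal of the participant (SAP 8.1) or of some values only (SAP 10.2.1, 16.1.4), and no sentence says which rule comes first.

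The data review meeting could put any of these right, but 9.3 gives it no criterion for departing from its own sentence. At stake would be the number of participants in the primary analysis, and whether the decision on that number could be checked.

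**Working it through.** **1. What a loss of participants would cost.** Protocol 9.2 states limits of 0.805 to 1.242 for N = 14, CV 20%, observed ratio 1.0, 90% CI and 80% probability. They are reproduced by

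h = t(0.95, N−2) × s × √(4/N) × √(χ²(0.80, N−2)/(N−2)), with s = √ln(1 + 0.20²) = 0.1980.

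- N = 14: 1.7823 × 0.1980 × 0.5345 × 1.1479 = 0.2166, so exp(±h) = 0.805 to 1.242. This matches.
- N = 12: 1.8125 × 0.1980 × 0.5774 × 1.1594 = 0.2403, giving 0.786 to 1.272, as in Table 4. The log half-width is 0.2403/0.2166 = 1.11 times that at N = 14.
- N = 18: h = 0.1843, giving 0.832 to 1.202, as in Table 4.

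This formula is the two-group form. A paired form, with √(2/N) and N−1 degrees of freedom, gives narrower limits: 0.859 to 1.164 at N = 14 and 0.846 to 1.182 at N = 12. The relative widening is almost the same (0.1675/0.1515, about 1.11).

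Going from 18 to 14 only reaches the planned precision. Precision falls below plan only if more than 18 − 14 = 4 participants are lost. These figures say what a loss would cost. They do not show that the rule causes one, because the documents give no exclusion rate.

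**2. Laxative.**

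| Reading | Excluded for the laxative | Left, if 18 are assigned |
|---|---|---|
| Literal: not on the permitted list, so prohibited | 18 | 0 |
| Scheduled dose is part of the protocol, so not prohibited | 0 | 18 |

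Section 6.8.3 restricts what participants may use. Section 8.4 and the Schedule tell the site what to give. The specific instruction governs the general ban, and a participant who follows 8.4 has not deviated.

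The laxative also falls on the third day of each period (Day 3 from dosing on Day 1, Day 14 from dosing on Day 12). In each period 5 of the 19 postdose samples in Table 1 (72, 96, 120, 144 and 168 h) come after it, or 6 if the 60 h sample is drawn later that evening. That bears on a possible effect on PK, matched between periods. It does not bear on set membership.

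**3. Window.** The ban outlasts sampling by Day 20 − Day 19 = about 1 day. Removing that day from 9.3 need not retain anyone. The PK set also requires completion of the study, Protocol 4.4 defines completion to include the Day 20 assessments, and Protocol 7.2 lists use of non-permitted medication among reasons for mandatory withdrawal. A medicine taken in that last day may therefore remove the participant by this other route.

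**4. Order.** The rules differ in scope. SAP 8.1 concerns prohibited items. SAP 10.2.1 concerns any concomitant medication, including what 6.8.2 allows, and its value-flagging is an example that does not rule out exclusion from the set. SAP 10.2.2 reports reasons for leaving the PK set separately from reasons for dropping single concentrations. SAP 16.1.4, on participants who withdraw early, makes their inclusion conditional on their still belonging to the PK set. Together these point to membership first, then values.

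**The case for a change.** The best case for a change is that the set for the primary analysis should not depend on a sensible reading. No text exempts the laxative or states the order. The trial is open-label, and 9.3 requires only that the decision precede database lock, without saying whether concentrations will have been seen. A few sentences would close the gap at almost no cost.

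The textual part stands: the exemption and the order are unwritten. The wording on non-permitted medicines also differs between Protocol 7.1, which ties stopping study intervention to clinical relevance, and 7.2, which has no such condition.

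The claim that the decision could not be checked does not stand. Reasons for exclusion from the PK set are listed (SAP 10.2.2), and concomitant medications are listed (SAP 12). Individual PK parameters are listed for the Safety set (SAP 16.1.6.1), so excluded participants' values remain visible. What remains is that no stated reason is required when someone is kept despite 6.8.3, but the medication listing would show that case.

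Extending the relevance test in 9.3 to prohibited medicines would not be a clear gain. In an open-label interaction study, a fixed rule for prohibited medicines leaves less room for judgement that might follow the results. Its price is an occasional needless exclusion.

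**Conclusion.** No change is needed. The gaps are in the drafting, and the data review meeting would fill them in the obvious way: the scheduled laxative is not a prohibited medicine, and set membership is settled before individual values. On that reading the laxative removes 0 participants, and the planned 14 to 18 evaluable are untouched. The window affects about one day, in which other criteria may apply anyway. No loss of precision can be attributed to the rule. Whether to keep the mechanical exclusion or add a relevance judgement is a fair trade-off that belongs to the sponsor.

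This rests on two assumptions: that the meeting treats a dose scheduled by the protocol as compliant, and that nothing in the redacted parts of Protocol 8.4 or SAP 16.1 says otherwise. No redaction is visible in Protocol 6.8.2, 6.8.3 or 9.3, or in SAP 8.1.

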9.4 Statistical Analyses

Statistical analysis will be performed using the computer program package SAS® System (release 9.2 or later version; SAS Institute, Cary NC, USA). More details on the statistical analysis will be presented in the IAP prior to database lock.

The statistical analysis will not be started until all data have been corrected and checked for plausibility, and until all necessary coding and assessments have been completed.

Medical history and AE terms will be coded with the latest version of MedDRA (Version 23.0 or later); concomitant medication will be coded with WHO Drug Dictionary, WHO Drug Reference List and Anatomical Therapeutic Chemical Classification System, latest versions. Versions of dictionaries used for coding will be defined in the Data Management Plan.

All data recorded during the study will be presented in individual data listings.

For demographic (e.g., age, sex, race, etc.), Baseline and safety assessments, continuous measurements will be summarized by means of descriptive statistics (i.e., number and percentage of observations, number and percentage of missing observations, mean, SD, median, the first and third quartile [Q1 and Q3], Min, and Max) and categorical data will be summarized by means of frequency tables (i.e., count and percentages), if not stated otherwise.

All data will be evaluated as observed, no imputation method for missing values. The handling of concentration values below the limit of quantification will be described in the IAP.

9.4.1 Efficacy Analyses

Not applicable.

9.4.2 Safety Analyses

All safety analyses will be performed on the Safety Analysis Set.

Reference #	Endpoint	Statistical Analysis
Primary		Not applicable
Secondary		
2 – Safety	Nature, occurrence, severity, and seriousness of TEAEs	AE counts and participants with AEs will be summarized for each treatment by SOC and PT. In addition, AEs will be tabulated and listed per participant and analyzed by severity and relationship to study intervention.
	Absolute values and changes in safety laboratory tests from time of first dose to end of study participation	Safety laboratory parameters will be listed for each participant including changes from Baseline and flags for measurements outside the reference ranges, where applicable. Laboratory parameters (hematology and clinical chemistry) will be summarized by time point including both absolute values and changes from Baseline.
	Single 12-lead ECGs evaluated by Investigator from time of first dose to end of study participation	ECG data will be summarized by absolute and changes from Baseline values by treatment using descriptive statistics. Clinical noteworthy ECG findings for individual participants will be listed and summarized as appropriate.
	Vital signs assessed from time of first dose to end of study participation	Vital signs by participant, including changes from Baseline, will be listed and summarized by treatment and time point using descriptive statistics.
CCI [REDACTED]		[REDACTED]

AE=adverse event; ECG=electrocardiogram; PT=preferred term; SOC=system organ class; TEAE=treatment-emergent adverse event.

9.4.3 Other Analyses

Analysis of Primary Endpoints

The effect of coadministration of itraconazole on tepotinib exposure will be assessed. A general linear model with a fixed effect for TREATMENT and a random effect for SUBJECT will be applied to the log-transformed PK parameters C_{max} , $AUC_{0-tlast}$ and $AUC_{0-\infty}$ based on the PK analysis set. Treatment differences on the log scale of tepotinib with itraconazole versus tepotinib alone (Day 12 versus Day 1) will be estimated for the C_{max} , $AUC_{0-tlast}$ and $AUC_{0-\infty}$ together with their 90% CIs. Point estimates and CIs will be back transformed to the original scale for presentation.

The analysis will be repeated with both SUBJECT and TREATMENT as fixed effects.

CCI [REDACTED]

[REDACTED]

CCI [REDACTED]

[REDACTED]

[REDACTED]

[REDACTED]

Appendix 1 Abbreviations

AE	Adverse event
AESI	Adverse events of special interest
ALP	Alkaline phosphatase
ALT	Alanine aminotransferase
AST	Aspartate aminotransferase
ATP	Adenosine triphosphate
BCS	Biopharmaceutical classification system
BMI	Body mass index
CI	Confidence interval
CIOMS	Council for International Organizations of Medical Sciences
COVID-19	Coronavirus disease 2019
CRF	Case report form
CRO	Clinical research organization
CRU	Clinical research unit
CSR	Clinical Study Report
CTFG	Clinical Trials Facilitation and Coordination Group
CV	Coefficient of variation
CYP	Cytochrome P450
DDI	Drug-drug interaction
DNA	Deoxyribonucleic acid
DSUR	Development safety update report
ECG	Electrocardiogram
eCRF	Electronic case report form
EDC	Electronic data capture
EudraCT	European Clinical Trials Database
FSH	Follicle-stimulating hormone
GCP	Good Clinical Practice
HGF	Hepatocyte growth factor
HIPAA	Health Insurance Portability and Accountability Act
HRT	Hormone replacement therapy

IAP	Integrated analysis plan
IB	Investigator's brochure
ICF	Informed consent form
ICH	International Council for Harmonization
IEC	Independent Ethics Committee
IRB	Institutional Review Board
IMP	Investigational medicinal product
INR	International normalized ratio
IRB	Institutional Review Board
LFT	Liver function test
Max	Maximum
MedDRA	Medical Dictionary for Regulatory Activities
MET	Mesenchymal epithelial transition factor
Min	Minimum
MR	Metabolic ratio
NSCLC	Non-small cell lung cancer
PCR	Polymerase chain reaction
CC	[REDACTED]
P-gp	P-glycoprotein
PK	Pharmacokinetic
QTcB	Corrected QT internal by Bazett's formula
QTcF	Corrected QT interval by Fridericia' formula
QTL	Quality tolerance limits
SAE	Serious adverse event
SAF	Safety
SARS-CoV-2	Severe acute respiratory syndrome coronavirus 2
SD	Standard deviation
SmPC	Summary of product characteristics
SoA	Schedule of assessments
SUSAR	Suspected unexpected serious adverse reactions
TEAE	Treatment-emergent adverse event

TF2/TF3	Tablet formulation 2/Tablet formulation 3
TSH	Thyroid stimulating hormone
ULN	Upper limit of normal
US	United States
USPI	United States prescribing information
WHO	World Health Organization
WOCBP	Woman of child-bearing potential

Appendix 2 Study Governance

Financial Disclosure

- Investigators and Sub-Investigators will provide the Sponsor with sufficient, accurate financial information, as requested, for the Sponsor to submit complete and accurate financial certification or disclosure statements to the appropriate regulatory authorities. This information is required during the study and for 1 year after completion of the study.

Informed Consent Process

- The Investigator or his/her representative will explain the nature of the study to the participant and answer all questions on the study.
- Participants will be informed that their participation is voluntary.
- Participants will be required to sign a statement of informed consent that meets the requirements of 21 CFR 50; local regulations; ICH guidelines; HIPAA requirements, where applicable; and the IRB/IEC or study center.
- The medical record will include a statement that written informed consent was obtained before the participant was enrolled in the study and the date the written consent was obtained. The authorized person obtaining the informed consent will also sign the ICF.
- If the ICF is updated during their participation in the study, participants will be reconsented to the most current, approved version.

Data Protection

- The Sponsor will assign a unique identifier to participants after obtaining their informed consent. Any participant records or datasets that are transferred to the Sponsor will contain the identifier only; participant names or any identifiable information will not be transferred.
- The Sponsor will inform participants that their personal study-related data will be used per local data protection and privacy laws. The level of disclosure will also be explained to the participant and pregnant partners (if applicable), who will be required to give consent for their data to be used, as specified in the informed consent.
- The participant will be informed that his/her medical records may be examined by Clinical Quality Assurance auditors or other Sponsor-appointed, authorized personnel, by appropriate IRB/IEC members, and by regulatory authority inspectors. All such persons will strictly maintain participants' confidentiality.

Study Administrative

- The Principal Investigator listed on the title page represents all Investigators for decisions and discussions on this study, per ICH GCP. The Principal Investigator will provide expert medical input and advice on the study design and execution and is responsible for the review and signoff of the clinical study report.
- The study will be conducted at a single center, the Clinical Pharmacology Unit of Nuvisan GmbH, Neu-Ulm, Germany. Nuvisan GmbH will be responsible for the following activities:

- Clinical conduct and laboratory services
- Data management
- Statistical programming and analysis
- PK analysis
- Medical writing
- Independent monitoring
- Medical monitoring
- Project management
- Regulatory services
- Clinical trial supplies will be provided by the Sponsor.
- Details of structures and associated procedures will be defined in a separate manual.

Regulatory and Ethical Considerations

- This study will be conducted in accordance with the protocol and the following:
 - Consensus ethical principles derived from international guidelines, including the Declaration of Helsinki and CIOMS International Ethical Guidelines
 - Applicable ICH GCP Guidelines
 - Applicable laws and regulations
- The protocol, protocol amendments (if applicable), ICF, Investigator Brochure, and other relevant documents (e.g., advertisements) will be submitted to an IRB/IEC for review and approval before the study is initiated.
- Any protocol amendments (i.e., changes to the protocol) will be documented in writing and require IRB/IEC approval before implementation of changes, except for changes necessary to eliminate an immediate hazard to study participants. When applicable, amendments will be submitted to the appropriate Health Authorities.
- The protocol and any applicable documentation will be submitted or notified to the Health Authorities in accordance with all local and national regulations for each site.

Emergency Medical Support

- The Sponsor or designee will provide Emergency Medical Support cards to participants for use during the study. These provide the means for participants to identify themselves as participating in a clinical study. Also, these give health care providers access to any information about this participation that may be needed to determine the course of medical treatment for the participant. The information on the Emergency Medical Support card may include the process for emergency unblinding (if applicable).
- The first point of contact for all emergencies will be the clinical study Investigator caring for the participant. Consequently, the Investigator agrees to provide his or her emergency contact

information on the card. If the Investigator is available when an event occurs, they will answer any questions. Any subsequent action (e.g., unblinding) will follow the standard process established for Investigators.

- When the Investigator is not available, the Phase 1 facility will provide the appropriate means to contact a physician. This includes the provision of a 24-hour contact number at the facility, whereby the health care providers will be given access to an appropriate physician to assist with the medical emergency and to provide support for the potential unblinding of the participant concerned.

Clinical Study Insurance and Compensation to Participants

- Insurance coverage will be provided for each country participating in the study. Insurance conditions will meet good local standards, as applicable.

Clinical Study Report

- After study completion, the Sponsor will write a clinical study report in consultation with the Principal Investigator and other relevant study-appointed experts of the Sponsor and Nuvisan GmbH.

Publication

- The results of this study may be published or presented at scientific meetings. If this is foreseen, the Investigator agrees to submit all manuscripts or abstracts to the Sponsor before submission. This allows Merck to protect proprietary information and to provide comments.
- The Sponsor will comply with the requirements for publication of study results. Per standard editorial and ethical practice, the Sponsor will generally support publication of multicenter studies only in their entirety and not as individual site data.
- Authorship will be determined by agreement and in line with International Committee of Medical Journal Editors authorship requirements.

Dissemination of Clinical Study Data

- A summary of data will be provided to ClinicalTrials.gov as well as to the European Clinical Trial Database, as applicable, and will occur 12 months after the last clinic visit of the final study participant or another appropriate date to meet applicable requirements. Healthy participants might be provided with the results of the medical examinations at request. After finalization of the study, healthy participants might be provided with the information published on ClinicalTrials.gov and/or the European Clinical Trial Database at request.
- After completion of the study, a clinical study report will be written by the Sponsor in consultation with the Principal Investigator following the guidance in ICH Topic E3 and will be submitted in accordance with local regulations.

- Any and all scientific, commercial, and technical information disclosed by the Sponsor in this protocol or elsewhere should be considered the confidential and proprietary property of the Sponsor. The Investigator shall hold such information in confidence and shall not disclose the information to any third party except to such of the Investigator's employees and staff who had been made aware that the information is confidential and who are bound to treat it as such and to whom disclosure is necessary to evaluate that information. The Investigator shall not use such information for any purpose other than for determining mutual interest in performing the study and, if the parties decide to proceed with the study, for the purpose of conducting the study.
- The Investigator understands that the information developed from this clinical study will be used by the Sponsor in connection with the development of the study intervention and therefore may be disclosed as required to other clinical Investigators, to the FDA, EMA, and to other government agencies. The Investigator also understands that, to allow for the use of the information derived from the clinical study, the Investigator has the obligation to provide the Sponsor with complete test results and all data developed in the study. No publication or disclosure of study results will be permitted except under the terms and conditions of a separate written agreement.

Data Quality Assurance

- All participant study data will be recorded on printed or electronic CRFs or transmitted to the Sponsor or designee electronically (e.g., laboratory data). The Investigator is responsible for verifying that data entries are complete, accurate, legible, and timely by physically or electronically signing the CRF. Details for managing CRFs are in the Data Management Plan.
- The Investigator will maintain accurate documentation (source data) that supports the information in the CRF.
- The Investigator will permit study-related monitoring, quality assurance audits, IRB/IEC review, and regulatory agency inspections and provide direct access to the study file and source data.
- QTLs will be predefined in the Operational Manual to identify systematic issues that can impact participant safety and/or reliability of study results. These predefined parameters will be monitored during the study and important deviations from the QTLs and remedial actions taken will be summarized in the clinical study report.

Note: QTLs will not be defined in this Phase I study as neither the limited number of planned participants nor the short duration of the study support the collection of meaningful QTLs.

- Monitoring details describing strategy (e.g., risk-based initiatives in operations and quality such as Risk Management and Mitigation Strategies and Analytical Risk-Based Monitoring), methods, responsibilities and requirements, including handling of noncompliance issues and monitoring techniques (central, remote, or on-site monitoring) are in the Monitoring Plan.
- The Sponsor or designee is responsible for data management of this study, including quality checking of the data and maintaining a validated database. Database lock will occur once quality control and quality assurance procedures have been completed. Details will be outlined in Data Management documents and procedures.

- Study Monitors will perform ongoing source data verification to confirm that data in the CRF are accurate, complete, and verifiable; that the safety and rights of participants are being protected; and that the study is being conducted per the currently approved protocol and any other study agreements, ICH GCP, and all applicable regulatory requirements.
- The Investigator will retain records and documents, including signed ICFs, pertaining to the conduct of this study for 15 years after study completion, unless local regulations, institutional policies, or the Sponsor requires a longer retention. No records may be destroyed during the retention period without the Sponsor's written approval. No records may be transferred to another location or party without the Sponsor's written notification.

Source Documents

- Source documents provide evidence for the existence of the participant and substantiate the integrity of the data collected.
- The Investigator will maintain source documents that support the data recorded in the CRFs.
- Data recorded on CRFs that are transcribed from source documents will be consistent with the source documents or the discrepancies will be explained. The Investigator may need to request previous medical records or transfer records, depending on the study. Also, current medical records will be available.
- Source documents are stored at the site for the longest possible time permitted by the applicable regulations, and/or as per ICH GCP guidelines, whichever is longer. The Investigator ensures that no destruction of medical records is performed without the Sponsor's written approval.
- Definition of what constitutes source data is found in the Source Data Location Form.

Study and Site Start and Closure

The study start date is when the first participant signs the Informed Consent Form.

Study and Site Closure

The Investigator may initiate site closure at any time, provided there is reasonable cause and enough notice is given in advance of the intended closure.

Reasons for the early closure of a study site by the Sponsor or Investigator may include:

- Failure of the Investigator to comply with the protocol, the requirements of the IRB/IEC or local Health Authorities, the Sponsor's procedures, or GCP guidelines
- Inadequate recruitment of participants by the Investigator
- Discontinuation of further development of the Sponsor's compound
- If the study is prematurely terminated or suspended, the Sponsor will promptly inform the Investigators, the IECs/IRBs, the regulatory authorities, and any third-party service providers of the reason for termination or suspension, as specified by the applicable regulatory requirements. The Investigator will promptly inform the participants and assure appropriate participant therapy and/or follow-up.

